Aim 2. To investigate whether there is a difference in adverse events during the treatment period with sealed shoe and TCC.

Aim 3. To investigate whether there is a difference in long-term effects (up to 12 months after end of treatment) with sealed shoe and TCC.

Aim 4. To investigate whether there is a difference in health economic outcomes between treatment with sealed shoe and TCC.

The null hypothesis is that a sealed therapeutic shoe does not heal DFUs as effectively as TCC, and that there are no differences between sealed shoe and TCC in adverse events, long-term effects and health economic outcomes.

Methods

The study is a non-inferiority multicenter randomized controlled trial (RCT).

Participants

Inclusion criteria: at least 18 years old, diagnosed diabetes mellitus (all types) and foot ulcer under metatarsal heads. A foot ulcer is here defined as "a break of the skin of the foot that includes minimally the epidermis and part of the dermis."¹⁵

Exclusion criteria: large ulcers (covering 3-5 metatarsal heads), toe pressure or TcPO₂ <30 mmHg, infection of IWGDF grade 3 (if uncontrolled or treatment has not been administered) or IWGDF grade 4, life expectancy <1 year, active Charcot foot, need of custom-made shoe,

and inability to read or write Swedish. In addition, people will be excluded where dementia, language- or other communication difficulties, active alcohol or substance abuse, or other factors increase the risk that adverse events will not be noted or reported, if the person does not have adequate social support.

The study is a randomized controlled non-inferiority trial where it will be investigated whether a new intervention (sealed shoe) is at least as effective as the established intervention (TCC).

Primary outcome is proportion of healed ulcers after 12 weeks of treatment. Based on the literature and our feasibility study the proportion of healed ulcers after 12 weeks treatment is estimated to 90% with sealed shoe or cast.^{16,17} If accepting $p=0.05$, a statistical power of 80% and a non-inferiority limit of 10%, 112 participants are needed. To compensate for attrition of participants, the aim is to recruit 150 participants. However, if it turns out that it is too difficult to recruit 150 participants, the recruitment of participant will end when the primary end point (healing at 12 weeks) has been observed for 56 participants per group, giving a total of 112 which fulfills the sample size calculation.

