The participants will be randomized to treatment with sealed therapeutic shoe or TCC. The randomization will be stratified for ulcer size (smaller or bigger than 1 cm^2 , ulcer size calculated as longest diameter*longest perpendicular diameter) and study center, and use random permuted blocks of randomly varying size.

Recruitment of participants

People who fulfill the inclusion criteria and not the exclusion criteria will be given oral and written study information and asked about whether they are interested in participating in the study. Those who agree will sign an informed constant to participate.

Intervention group, sealed therapeutic shoe: A prosthetist/orthotist will try out new therapeutic shoes to the participants and make individual insoles after casts of the feet. There will a limited number of shoe types to choose between and the procedure and material for the insole production will be standardized. The ulcer will be offloaded by adjusting the insoles with the help of plantar pressure measurement using the F-scan system (Tekscan, Boston, MA, USA). The “seal” of the shoe consists of a soft plastic strip (Bracelok, DJO Nordic, Malmö) that have to be broken to remove the shoe.

[figure not shown]
Control group, TCC: The participants will be treated with TCC, applied in a standardized manner. Participants in this group will also receive shoes and insoles, according to the same protocol as above, before TCC treatment is initiated to be comparable to the other group in the long-term follow-up after healing, when both groups will use shoes and insoles to prevent reulceration.

Both groups will visit the cast technician 1-2 times/per week depending on the status of the ulcer. The cast technician will change dressings, note whether the seal has been broken (for the intervention group), change casts (for the control group), photograph and document ulcers and complications, and ask participants if they have experienced any issues with the treatment. After this, a new dressing is applied, and the shoe is sealed (intervention group) or

a new cast is applied (control group). Participants will use a cover on the shoe or cast while taking a shower, and for the intervention group a cover will also be used when sleeping. Both groups will receive written information about potential complications and contact information to the clinics.

Data collection

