Participants in both groups will be assessed by a physiotherapist on five occasions (Figure 1): at base-line, four weeks into the treatment period, and then 1, 6 and 12 months after healing (when treatment is ended). For the 4 week into treatment and 1 month post-treatment assessments, a visit window of ± 1 week will be used. For the 6 and 12 months post-treatment assessments, a visit window of ± 1 month will be used. Standardized and validated instruments and assessment methods will be used for the data collection (Table 1).

Aim 1: Ulcer healing (primary end point)

Primary outcome measure is ulcer healing after 12 weeks of treatment, defined by the Food and Drug Administration (FDA) as full skin epithelization of the ulcer, confirmed by a second observation 14 days later.¹⁸ The cast technicians will assess ulcer healing in both the intervention group and control group. They will also photograph the ulcer and healed skin so a person blinded to group allocation can assess ulcer healing afterwards.

Aim 2: Adverse events during treatment (secondary end points)

Adverse events that are judged to be related to the offloading devices (shoe or TCC) will be classified as adverse device effects (ADE) and serious adverse device effects (SADE).³² ADE include, but are not limited to, skin abrasions, blisters, sleep disturbances, issues with gait and balance, etc. SADE include, but are not limited to, new foot ulcers that result in amputation (major amputation = above ankle, minor amputation = below ankle), sepsis, etc.

Adverse events that are not related to the offloading devices are classified as adverse events (AE) and serious adverse events (SAE).³² AE include, but are not limited to, skin abrasions, new foot ulcers on the contralateral foot and not related to the device, etc. SAE include, but are not limited to, death, amputation, onset of acute Charcot foot, sepsis, etc. (not related to the offloading device). However, in accordance with previous studies on this patient population, the investigators choose not to include all AE and SAE as the patient population suffers from multiple co-morbidities and therefore a high incidence of illness and hospital admissions unrelated to the DFU and offloading devices can be expected.³³ Therefore, all

ADE and SADE will be assessed, but only certain types of AE and SAE that are of particular interest, such as, amputation, death and onset of acute Charcot foot.

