ADE, SADE, AE and SAE will be assessed with the aid of questionnaires, case report form (CRF), photographs of ulcer and skin, and patient files.

Aim 3: Long-term effects (secondary end points)

The secondary endpoints are time to healing and measures listed in Table 1. Each secondary endpoint is measured between one and five occasions during the study. For example, incidence of new foot ulcers, amputation, onset of acute Charcot-foot, death, adherence to using therapeutic shoes and locus of control will be assessed. Our hope is that the positive experience in the intervention group of that using therapeutic shoes can heal ulcers will result in a stronger internal locus of control and higher adherence to using therapeutic shoes after healing, so that fewer people will reulcerate or be affected by foot complications in the long term.

Data from patient files, questionnaires and the physiotherapists' assessments will be used for the analysis.

Aim 4: Health-economic outcomes (secondary end points)

The questionnaires RAND-36 and EQ-5D-5L will be used to assess general quality of life. Data from patient journals, Swedish Social Insurance Agency's system, and self-report questionnaires will be used to assess health care consumption and other costs.

Statistical analysis

See separate document for statistical analysis plan.

Research ethics

The participants will be informed about risks of the interventions in the written information that also will include contact information for the clinics. Risks will be minimized by excluding certain patient groups with heightened risks of side-effects not being noted or reported, and by a frequent follow-up during the intervention period. The study has been approved by the region ethics review board in Uppsala, Sweden (documents 2018/387 and 2019-03512).

Table 1. Overview of variables and assessment methods.

Variable	Assessment method	Assessment occasion					Specific aim
		Treatment period		Follow-up after treatment end			
		Base-line	4 weeks	1 month	6 months	12 months	
Ulcer healing	Clinical observation + blinded photo assessment	X	X	X			1
Skin complications	Clinical observation + blinded photo assessment	X	X	X			2
Glycemic control	Blood sample (HbA1c) ^a	X	X	X	X	X	2,3
BMI	Measurement of weight and height	X	X	X	X	X	2,3
Gait function	10 meter walk test ^{b 19}	X	X	X	X	X	2,3
Gait function	Timed up and go ^{b 20}	X	X	X	X	X	2,3
Balance	Berg balance scale ^{b 21}	X	X	X	X	X	2,3

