2.6 TIMING OF FINAL ANALYSIS

The short-term outcomes, that is, healing, adverse events and adverse device effects during treatment, will be analyzed and published after the required number of participants have ended the treatment period.

The long-term outcomes, that is, up to 12 months after treatment end, will be analyzed and published after that every included participant has either been assessed for 12 months outcomes or has been lost to follow-up.

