2.7 TIMING OF OUTCOME ASSESSMENTS

Table 1 below lists outcomes and time points for assessments (base-line, 4 weeks into treatment, and 1, 6 and 12 months after treatment end). For the 4 week into treatment and 1 month post-treatment assessments, a visit window of ± 1 week will be used. For the 6 and 12 months post-treatment assessments, a visit window of ± 1 month will be used.

Table 1. Overview of variables and assessment methods.

Variable (scale level: nominal=N, ordinal=O, interval=I)	Assessment method	Assessment occasion				
		Treatment period		Follow-up after treatment end		
		Base- line	4 weeks	1 month	6 months	12 months
Ulcer healing (N)	Clinical observation + blinded photo	X	X	X		
Skin complications (N)	Clinical observation + blinded photo	X	X	X		
Glycemic control (I)	Blood sample (HbA1c) ^a	X	X	X	X	X
BMI (I)	Measurement of weight and height	X	X	X	X	X
Gait function (I)	10 meter walk test ^{b 17}	X	X	X	X	X
Gait function (I)	Timed up and go ^{b 18}	X	X	X	X	X
Balance (O)	Berg balance scale ^{b 19}	X	X	X	X	X
Muscle atrophy (I)	Calf circumference ^{a 20}	X	X	X	X	X
General quality of life (O)	RAND-36 ^{c 21} , EQ-5D-5L ^{c 22}	X	X	X	X	X
Disease-specific quality of life (O)	DFS-SF ^{c 23}	X	X	X	X	X
Physical activity (I)	ActivPAL ^{d 24}	X	X	X	X	X
Physical activity (O)	National Board of Health and Welfare's indicator questions ²⁵	X	X	X	X	X
Bone mass density (I)	DXA ^e (heel bone)	X		X	X	X
Locus of control (O)	Questions from MHLC-C ^{c 26}	X		X	X	X
Ankle range of motion (I)	Goniometer ^{a 27}	X		X	X	X
Ankle strength (I)	Dynamometer ^{a 28}	X		X	X	X
Adherence to therapeutic shoes (O)	Questions from Q-TFA ^{c 29}	X		X	X	X
Treatment satisfaction (O)	Visual analogue scale ^c		X	X		
New ulcers, amputations, death, Charcot foot (N)	Patient file and self-report ^c				X	X
Health care consumption (O) ^f	Patient administration systems and self-report ^c			X	X	X
Sick leave from work (I) ^f	Self-report, ^c Swedish Social Insurance Agency's system			X	X	X

^aStandardized method, ^bfunction test, ^cquestionnaire, ^dactivity monitor, ^eDual-energy X-ray absorptiometry ^ffor the of health-economic analysis.

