6.1.2 ANALYSIS OF THE SECONDARY ENDPOINT(S)

The secondary analyses are not dependent on the findings of the primary endpoint. No adjustment for Type 1 errors will be used as only one or a few statistical tests will be conducted for each secondary endpoint.

The secondary endpoints are time to healing and measures listed in Table 1. Each secondary endpoint is measured between one and five occasions during the study. The ITT dataset will be used for all analyses of secondary endpoints. Adjusted analyses will only be conducted for certain secondary endpoints that are of particular interest.

Time to healing will be compared between the study groups using survival analysis. Kaplan-Meier survival curves will be produced for the two study groups with median healing times and 95 % CI. Participants for whom the ulcer has not healed will be treated as censored and their date of trial exit or date of last available assessment will be used to calculate their duration in the trial. Hazard ratio with

95% CIs will be presented. Treatment effect will be explored using a Cox proportional hazards model including stratification factors (ulcer area and depth at baseline, periphery artery disease and infection grade) initially.

Survival analysis as above (but without adjustment) will also be used to compare ulcer recurrence after healing between the study groups. Recurrence rates at 12 months after healing will also be compared.

The analysis of the other secondary endpoints will be conducted according to scale level (nominal, ordinal or interval; Table 1) and compared at each time point (base-line, 4 weeks into treatment and 1, 6 and 12 months post-treatment) using the ITT dataset without adjustment for covariates: t-tests for ordinal and interval data if the assumptions of the t-test is fulfilled (normal distribution and equal variances), otherwise Wilcoxon rank sum test will be used. The Chi-squared test or generalized linear regression method will be used for nominal scale data. For each comparison both exact p-values and two-sided 95% CI will be reported.

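### Long-term visits are counted from healing in one place and from treatment end in others, so never-healed participants have no defined 1, 6 and 12-month visits and Aim 3 comparisons called ITT may become conditional on healing

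*Protocol*

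**What the plan says.** The protocol's Data collection section lists five physiotherapist assessments: baseline, four weeks into treatment, "then 1, 6 and 12 months after healing (when treatment is ended"). Its description of the control group likewise speaks of "long-term follow-up after healing, when both groups will use shoes and insoles to prevent reulceration".

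Elsewhere the starting point is the end of treatment, with no mention of healing. Aim 3 concerns "long-term effects (up to 12 months after end of treatment) with sealed shoe and TCC". The column heading in the protocol's Table 1 is "Follow-up after treatment end". SAP 2.7 lists "base-line, 4 weeks into treatment, and 1, 6 and 12 months after treatment end". SAP 2.6 and 6.1.2 also count from the end of treatment.

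For the long-term outcomes the protocol says that "incidence of new foot ulcers, amputation, onset of acute Charcot-foot, death, adherence to using therapeutic shoes and locus of control will be assessed". SAP 6.1.2 states: "The ITT dataset will be used for all analyses of secondary endpoints"; SAP 3.3 defines that dataset as everyone randomised. SAP 2.6 schedules the long-term analysis "after that every included participant has either been assessed for 12 months outcomes or has been lost to follow-up". SAP 6.2 gives a missing-data method for the primary outcome only.

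**The concern.** If the long-term clock starts at healing, a participant whose ulcer never heals has no time zero. Entry to the 1, 6 and 12-month comparisons then depends on an event after randomisation, and that event is the trial's primary outcome. An analysis restricted in this way is not ITT, whatever its label.

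The primary analysis uses a non-inferiority limit of 10 percentage points. If the shoe heals somewhat fewer ulcers, more of its poor-outcome patients fall outside the long-term comparison and its long-term results look better than they are. If TCC heals fewer, the error runs the other way. Aim 3 is a two-sided superiority comparison (SAP 1.2 and 2.4), so such a shift bears directly on what it claims. A visit that was never held cannot be recovered later.

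**Working it through.** **Step 1: who has a time zero under each wording.** The only text that says when treatment ends is the protocol's Data collection section, which equates it with healing. Neither document sets a maximum treatment period or an end of treatment for an ulcer that stays open.

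| Participant | Counted from healing | Counted from treatment end |
|---|---|---|
| Heals by week 12 | defined | defined, same date |
| Heals later | defined | defined, same date |
| Stops treatment unhealed | none | a date could be assigned; the plan does not say which |
| Remains unhealed and in treatment | none | none while treatment continues |

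In the last row, a participant still in contact has neither a 12-month assessment nor a loss to follow-up, so the condition in SAP 2.6 is not met.

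**Step 2: which outcomes depend on the anchor.** Gait, balance, bone density, ankle measures, quality of life, locus of control and shoe adherence need a visit or questionnaire, so they are the most exposed. New ulcers, amputation, death and Charcot foot come from patient files as well as self-report, but Table 1 marks them only in the 6 and 12-month columns, which share the anchor. Safety comparisons (SAP 6.1.3) cover the treatment period. An amputation after an unhealed participant has stopped the device therefore has no defined long-term window under the healing anchor. The health-economic horizon in SAP 6.1.2 ends 12 months after treatment end, so for these participants it has no defined close either.

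**Step 3: how many.** The plan gives no count of participants without long-term visits, so there is no figure to reproduce. Inputs: 90% healing at 12 weeks in both arms and the target of 150 (sample size text in both documents), and 1:1 allocation (SAP 2.1), hence 75 per arm. The 112 and 150 serve only as head counts here.

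- Unhealed at week 12 = N × (1 − healing rate).
- 90% in both arms: 75 × 0.10 = 7.5 per arm, 15 of 150. With 56 per arm: 5.6 per arm, about 11 of 112.
- Shoe 80%, TCC 90%: 75 × 0.20 + 75 × 0.10 = 15 + 7.5 = 22.5 of 150.
- Other equal rates (assumed): 95% gives 150 × 0.05 = 7.5; 70% gives 150 × 0.30 = 45.

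All are upper bounds, because an ulcer that heals after week 12 gets a date.

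**Step 4: effect on an event comparison.** The documents give no event risks. Assume a one-year risk of amputation or death of 3% in healed participants, and 30% or 15% in unhealed, the same in both arms. Treat all week-12 non-healers as never healed.

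Risk in all randomised = h × 3% + (1 − h) × risk in unhealed, where h is the proportion healed.

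| Healing, shoe v TCC | Risk in unhealed | All randomised, shoe v TCC | Difference | Healers only |
|---|---|---|---|---|
| 80% v 90% | 30% | 2.4 + 6.0 = 8.4% v 2.7 + 3.0 = 5.7% | 2.7 points | 3% v 3% |
| 80% v 90% | 15% | 2.4 + 3.0 = 5.4% v 2.7 + 1.5 = 4.2% | 1.2 points | 3% v 3% |
| 90% v 90% | 30% | 5.7% v 5.7% | 0 | 3% v 3% |

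**Step 5: effect on a continuous outcome.** If never-healed participants score k standard deviations worse and healed participants do not differ by arm, the hidden difference is (0.20 − 0.10) × k. For assumed k of 0.25, 0.5 and 1.0 this is 0.025, 0.05 and 0.10 SD.

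**The case against.** The strongest reply is that the healing anchor is largely one phrase. Aim 3, both Tables 1 and SAP 2.6, 2.7 and 6.1.2 all use treatment end. SAP 3.2, 4.3 and 4.4 foresee participants who discontinue or refuse treatment, so treatment can end without healing. SAP 2.6 expects every included participant to be assessed or lost, which does not read like a planned exclusion. This stands. A reader might infer that the plan removes unhealed participants from long-term follow-up; the documents do not say so. They contain two anchors and leave one undefined for this group. The reply does not close the gap, because nothing fixes the treatment-end date for a never-healed ulcer, and sites following different sections could follow different patients.

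Second, amputation, death and acute Charcot foot are named events of interest, drawn from case report forms and patient files, and compared between arms in the safety analysis on the ITT dataset. So the inference that such events in unhealed participants are lost is also too strong. What remains is the period after an unhealed participant leaves treatment, and the measures that need a visit.

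Third, the size rests on assumptions. At the plan's own 90% in both arms, with equal risks, the contrast is unbiased. That also stands. It leaves a result restricted to healed participants under an ITT label.

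Finally, the protocol cites a Figure 1 for the schedule, and it could not be read here. A rule for non-healers shown there would narrow the point, but the text would still need aligning.

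**Conclusion.** The anchors conflict, and treatment end is undefined for never-healed ulcers. Under the protocol's Data collection wording, Aim 3 comparisons called ITT become conditional on the primary outcome. At most about 15 of 150 participants are affected at the planned healing rate, and 22 to 23 at 80% v 90%; late healing lowers both.

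Bias in the treatment contrast needs healing, or the kind of patient who does not heal, to differ between arms. In the illustration at 80% v 90%, a true difference of 1.2 to 2.7 points shows as zero among healers, given the assumed risks, equal risks across arms and no late healing. For continuous outcomes the hidden difference is at most 0.10 SD over the range tried.

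A reader might conclude that Aim 3 cannot support a claim of better long-term effects. That goes too far: a healing-anchored comparison describes healed participants, and recurrence is properly a question about them. It should not be presented as a comparison of everyone randomised. The primary analysis is untouched. This is a cheap improvement.

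**What to change.** 1. Reconcile the healing anchor in the protocol's Data collection section with the treatment-end anchor in SAP 2.6 and 2.7. This point takes no position on when treatment should stop; it asks only that the visit schedule not depend on an undefined date.
2. In SAP 6.1.2, compare amputation, death, Charcot foot and new ulcers from patient files in all randomised participants, from randomisation to one common time point.
3. Give participants who have no healing date a fixed time, counted from randomisation, for the 6 and 12-month assessments, whatever treatment is then in use. Late healers keep their healing-anchored visits. Do not switch everyone without confirmed healing by week 12 to a week-12 anchor: late healers would then have two time zeros, and the 14-day confirmation would blur who belongs where. State which record counts if someone heals after a fixed-time visit.
4. Label healing-anchored comparisons as being in healed participants, not ITT, and align SAP 2.6 so that never-healed participants have a defined completion point.

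The cost is wording in both documents and a small number of extra visits, using staff and patient-file access already planned. The drawback is that visits in non-healers will not fall at the same time since healing as in the others.
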